Biofluid and tissue microbiome analysis: DNA will be extracted from each blood, saliva and lung tumor tissue sample using the QIAamp® UCP Pathogen Mini Kit (Qiagen) with extended homogenization of the tissue samples using the Mini-Beadbeater-96 cell disrupter (Biospec Products). The quantity and quality of the DNA extracts will be determined using a DeNovix DS-11 FX+ Spectrophotometer/Fluorometer and Agilent 4200 TapeStation, respectively. The DNA will then be prepared for shotgun metagenomic sequencing using the Nextera® DNA Flex Library Preparation Kit (Illumina). DNA libraries will be normalized and quantified prior to pooling to ensure equal library representation. Pooled DNA libraries will then be sequenced using the Illumina NovaSeq 6000 S1 Reagent Kit and sequencer, generating 2 x 150 bp paired-end reads. Raw sequence reads (FASTQ files) will be imported into the Microbial Genomics Pro Suite within the CLC Genomics Workbench (version 11.0.1; <https://www.qiagenbioinformatics.com>) for QC, adapter trimming, and analysis. High-quality ($\geq Q30$) reads for each sample will be aligned to those in a blank extraction sample (negative control) that will be processed from DNA extraction through library preparation to identify and remove contaminating sequences. The filtered reads will then be aligned to a reference database consisting of complete genomes in the RefSeq database for prokaryotes (bacteria and archaea), eukaryotes (fungi and protozoa) and viruses for taxonomic profiling. The filtered reads will also be assembled into contigs *de novo*, and MetaGeneMark (20) will be used to identify protein-coding regions within the reads to predict functional diversity of the microbiota identified in the samples. The coding regions will be annotated with Pfam domains

Pilot Study: Metabolic and microbial profiling of lung cancer
Wake Forest Baptist Comprehensive Cancer Center (WFBCCC)
WFBCCC # 03219

and GO terms, and the abundance of functional categories will be estimated to build a functional profile for each sample.

The results from the taxonomic and functional profiling will each be merged to estimate similarities and differences among the samples. Heat maps will be generated using Euclidean distance and clustering based on average linkage to assess functional similarities between samples, and principal component analysis (PCA) ordination of Bray-Curtis similarity between samples will be used to visualize the microbiota diversity across the samples.

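### No listed step removes human reads before de novo assembly, so human sequence can be annotated and tested as microbiota function

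*Combined protocol and SAP*

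**What the plan says.** The pipeline is in Section 4.2.2, under the paragraph on biofluid and tissue microbiome analysis.

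- **Material:** "DNA will be extracted from each blood, saliva and lung tumor tissue sample".
- **Sequencing:** "The DNA will then be prepared for shotgun metagenomic sequencing". There is no marker-gene amplification.
- **Generic processing:** the raw reads go into a named software suite "for QC, adapter trimming, and analysis", with a Q30 quality threshold.
- **Filter on origin:** reads are compared with a blank extraction carried through the same preparation, "to identify and remove contaminating sequences". What survives is called the filtered reads.
- **Taxonomic arm:** the filtered reads are aligned to "complete genomes in the RefSeq database for prokaryotes (bacteria and archaea), eukaryotes (fungi and protozoa) and viruses for taxonomic profiling".
- **Functional arm:** "The filtered reads will also be assembled into contigs", followed by MetaGeneMark gene calling, Pfam and GO annotation, and estimation of functional-category abundance for each sample.

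The data-generation paragraph of the same section describes the same two arms more briefly. Neither paragraph mentions alignment to a human genome, depletion of host DNA, reporting of the host read fraction, or the denominator for functional abundance.

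Section 6.3 then tests each marker pre- against post-surgery by paired t-test, on the hypothesis that markers related to lung cancer change and the others do not. Section 6.1 makes no multiplicity adjustment and uses the effect sizes to rank markers for future studies.

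**The concern.** All three sample types are of human origin, and shotgun sequencing reads whatever DNA the extract contains. A blank extraction can identify reagent and handling contamination. It does not represent the patient's genome, and at most it removes human reads that happen to match stray human sequence in the blank. Quality and adapter steps act on how well a read was sequenced, not on its source.

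The functional arm takes the blank-filtered reads, not the reads that matched a microbial genome. Nothing listed therefore stops human contigs from being gene-called and counted as microbial function.

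Two consequences follow. First, part of a functional profile may describe the patient. Second, if host share moves systematically between visits, many functional categories can move together with no change in the microbes. Section 6.3 would read such movement as a link with lung cancer, and the unadjusted ranking in Section 6.1 could carry it forward. Because the activities table in Section 4.3 has tumour collected once, the second consequence can arise only in saliva and blood. For tumour, varying host share would affect comparisons between patients: the stage models, the clustering and the Euclidean-distance heat maps.

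**Working it through.** **1. The plan's own figure.** Section 6.1 gives 80% power for 0.30 SD with 90 pairs, two-sided alpha 0.05. The noncentrality is 0.30 × √90 = 2.846. The noncentral t with 89 df gives 80.4%, and the normal approximation 81.2%. The detectable difference at 80% is 0.299 SD. The figure reproduces and is not in dispute; it serves as a yardstick below.

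**2. Following a human read through the listed steps.**
- Trimming and Q30: it passes if it is of good quality.
- Blank filter: it passes unless the blank happens to contain matching human sequence.
- Taxonomic alignment: it is mostly not counted, because no human genome is in the listed reference set. It can still mis-align to a listed genome.
- Assembly, gene calling, annotation: it goes in. No later step screens it out.

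**3. What can be said about size.** The documents do not give the host share of reads (h), the yield of called genes per host read relative to a microbial read (r), the abundance denominator, or the within-patient SD. All values of these below are assumptions. The microbial community is held unchanged throughout.

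*Host part of the functional profile*, as a share of called genes: r·h / ((1−h) + r·h). At h = 0.90:
- r = 0.01: 0.009/0.109 = 8%
- r = 0.1: 0.09/0.19 = 47%
- r = 1: 0.90/1.00 = 90%

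*Apparent change per total read:* R = (1−h_post)/(1−h_pre).
- 0.60 to 0.70: 0.30/0.40 = 0.75, a fall of 25%
- 0.50 to 0.60: 0.40/0.50 = 0.80, a fall of 20%
- 0.90 to 0.80: 0.20/0.10 = 2.00, a doubling

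*Apparent change per called gene:* the ratio of s(h) = (1−h)/((1−h) + r·h) at the two visits. For 0.90 to 0.80:
- r = 0: 1.00, no distortion
- r = 0.01: 0.962/0.917 = 1.05
- r = 0.1: 0.714/0.526 = 1.36
- r = 1: 0.20/0.10 = 2.00

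The same host shift thus gives anything from no distortion to a doubling.

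**4. What a systematic shift would do to the paired t-test.** Take the per-total-read denominator, n = 90, and an assumed SD of the within-patient log ratio of 0.5 to 1.0. The spurious effect is |ln R|/SD.
- Mean shift 0.50 to 0.55: R = 0.90, |ln R| = 0.105; effect 0.21 to 0.11 SD; rejection rate 51% to 17%.
- Mean shift 0.50 to 0.60: R = 0.80, |ln R| = 0.223; effect 0.45 to 0.22 SD; rejection rate 99% to 55%.

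The nominal rate is 5%, and the plan's detectable effect is 0.30 SD.

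**5. After the fix.** With host reads fully removed and abundance expressed per non-human read, an unchanged category has a ratio of 1.00 whatever h does. No sample-size or power figure changes.

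**The case against.** The strongest reply is that this is a short methods summary. It names a software suite without listing its settings, so a human filter may be routine in the laboratory. It also names a pathogen DNA extraction kit, and the documents do not settle whether that kit depletes host DNA. Silence is not a decision to keep human reads. This stands as a limit on certainty: one sentence from the laboratory could close the point. It does not remove the point, because the text defines which reads are filtered and sends exactly those to assembly. A section that states kits, a software version and a quality cut should state this step too.

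A second reply is that a percentage dilution is produced by the choice of denominator. In the taxonomic arm, dividing by reads matched to microbial genomes removes that dilution without any host filter. This is correct, and it is why the denominator belongs in the fix. It does not help the functional arm, where human genes may be in both numerator and denominator.

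A third reply is that no reason is given for host share to move in one direction. Variation with mean zero adds noise to a paired test and does not bias it. This also stands: the false-positive rates above apply only if the mean shifts.

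Finally, blood is optional and tumour has no second sample, so saliva is the only required paired microbiome sample. The affected analyses are secondary and described as hypothesis generating.

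**Conclusion.** The concern holds for the pipeline as written. The only source-based filter before assembly does not represent the patient's genome, so human reads from saliva, optional blood and tumour can be annotated as microbiota function. The exposure lies mainly in the functional arm; the taxonomic arm is partly screened by its reference set.

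A reader might infer more: that human reads are certain to dominate the profiles, or that every functional category and taxon will be off by a quarter or more between visits. The documents do not support this. They give no host share, gene yield, denominator or evidence of a directional shift, and they do not settle whether extraction depletes host DNA. A uniform fall in all microbial categories follows only with an all-reads denominator. The figures above show what is possible under stated assumptions, not what to expect.

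The primary feasibility objective, the sample size and the stated power are unaffected. The change should be made because the functional results feed an unadjusted ranking meant to guide later studies.

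**What to change.** Add to the microbiome analysis paragraph of Section 4.2.2:

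1. Before taxonomic alignment and assembly, align reads to a human reference genome and discard matches. Whether this comes before or after the blank filter matters little.
2. Express taxonomic and functional abundance per non-human (microbial) read, and state this denominator.
3. Report the host read fraction for each sample and visit, so that a systematic shift between visits or across stages can be seen. Removal does not restore microbial sequencing depth lost to host reads, which is a further reason to report it.

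If the laboratory already filters human reads, or the extraction depletes host DNA, say so and still give items 2 and 3.

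The cost is one computational step, which can be run on the stored FASTQ files, and a few sentences of text. No new samples, visits or assays are needed. The downside is the loss of a few true microbial reads that resemble human sequence.

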4.3 Study-Related Activities

	Pre-Study	Pre-surgery Collection	Surgical tumor removal	Post-Surgery Follow-up
Informed consent	X			
Demographics	X			
Medical history	X			
Pulmonary Function Tests (PFTs)		X		
Concurrent meds	X			X
Smoking Status		X		X
Breath Collection (EBC ^a /EBV ^b)		X		X
Saliva collection ^c		X		X
Blood collection ^d		X		X
Urine collection ^e		X		X
Tumor collections			X	
Adverse event evaluation		X		X

^a Approximately 1-1.5 mL of EBC will be generated in 10 min of breathing

^b 500 ml of EBV in each of 4 collection tubes will be collected in 5-7 min of breathing

^c 2 ml minimum of saliva will be collected into SalivaBio Passive Drool collection tubes

^d 5-10 ml blood sample in each redtop and purple top vacutainer blood collection tube

^e 25 ml minimum of urine will be collected in sterile specimen containers

5.0 Outcome Measures

5.1 Primary Outcomes

5.1.1 Since the primary objectives is to assess the feasibility of adding these non-invasive sample collections to pre- and post-surgery visits the following outcomes (counts) will be gathered to examine this:

5.1.1.1 Number of patients who are screened for trial

Pilot Study: Metabolic and microbial profiling of lung cancer
Wake Forest Baptist Comprehensive Cancer Center (WFBCCC)
WFBCCC # 03219

- 5.1.1.1.1 Among those screened, the number who are eligible
- 5.1.1.1.2 Among those eligible, the number who consent to participate
- 5.1.1.1.3 Among those who participate, the number who provide pre-surgery samples
- 5.1.1.1.4 Among those who provide pre-surgery samples, the number who provide post-surgery samples

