2.0 Objectives

Pilot Study: Metabolic and microbial profiling of lung cancer
Wake Forest Baptist Comprehensive Cancer Center (WFBCCC)
WFBCCC # 03219

This pilot study will establish non-invasive sample collections, including breath, saliva, blood and urine pre-surgery and at the patient's one-month post-surgery follow-up visit. Patients with suspected non-small cell lung cancer (NSCLC) stage I-III will be recruited from Co-I [name]'s clinic.

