2.1 Primary Objective

2.1.1 To evaluate the feasibility of adding non-invasive sample collections in the pre-surgical setting and at the post-surgery follow-up visit.

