6.0 Analytic Plan

6.1 Sample Size and Power

This is a pilot study therefore; many of the objectives are exploratory in nature. With this in mind, we plan to recruit two cohorts of patients with this study, 45 female and 45 males. In order to be able to examine the questions concerning the possible relationships of metabolic and microbial signatures over time and with lung cancer outcomes, both pre- and post- surgery measures are needed. Therefore, each patient must provide both a pre- and post-surgery sample (optional blood will be allowed) in order to be used in the signature analyses. If a post collection is not performed or collection is unsatisfactory, the patient will be replaced. Therefore, our target sample size of 90 patients (45 male/45 female) is the target for patients with both pre- and post- samples collected.

Pilot Study: Metabolic and microbial profiling of lung cancer
Wake Forest Baptist Comprehensive Cancer Center (WFBCCC)
WFBCCC # 03219

First, for the primary objective of assessing feasibility, we can determine the total number of patients needed in order to enroll 90 patients. To examine this question we will determine 1) the number of patients screened for the trial, 2) among those screened, the number who are eligible, 3) among those eligible, the number who consent to participate, 4) among those who participate, the number who provide pre-surgery samples, and 5) among those who provide pre-surgery samples, the number who provide post-surgery samples. Based on our design we will enroll patients until 90 provide pre- and post- surgery samples.

Since we do not know prospectively how many patients will be needed to enroll 90 we will conservatively estimate several possible scenarios and for each scenario describe the width of the corresponding 95% Exact Clopper Pearson confidence interval for proportions.

The table below shows different total number of patients needed to enroll 90 for the study, beginning with 120 (75% enrollment rate) to 180 (50% enrollment rate).

# screened and eligible	Number enrolled	Enrollment rate	Lower 95% limit	Upper 95% limit
120	90	75%	0.66	0.82
150	90	60%	0.52	0.68
180	90	50%	0.42	0.58

As can be seen from the above, the confidence intervals for each scenario are approximately +/- 10% or less depending on the scenario observed.

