6.2 Analysis of Primary Outcome

To examine the questions of feasibility, we will generate a series of estimates of proportions for each question (i.e. proportion of screened who are eligible, etc.). Next, we will estimate 95% exact Clopper-Pearson confidence intervals for each feasibility estimate.

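### The primary feasibility outcome pools five collections into one undefined sample count per visit, so it cannot show which collections are feasible, and one failed collection could cost a patient's other valid pairs

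*Combined protocol and SAP*

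**What the plan says.** The primary objective (2.1.1) is "To evaluate the feasibility of adding non-invasive sample collections in the pre-surgical setting and at the post-surgery follow-up visit". Section 2.0 lists what is collected: "This pilot study will establish non-invasive sample collections, including breath, saliva, blood and urine pre-surgery", and again at the one-month follow-up. Section 4.3 divides breath into EBV and EBC and schedules all five collections at both visits. Section 4.2.2 shows that their burdens differ: a mask device for 5-7 minutes (EBV), a separate tube for 10 minutes (EBC), passive drool, a urine cup, and a blood draw that the patient may decline because it could be felt to be invasive.

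The primary outcome is a recruitment funnel whose last two steps concern collection: "Among those who participate, the number who provide pre-surgery samples" (5.1.1.1.3) and "Among those who provide pre-surgery samples, the number who provide post-surgery samples" (5.1.1.1.4). Section 6.2 plans one proportion with an exact Clopper-Pearson interval for each step. No section defines who counts as a provider, and none plans a count by specimen type.

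Section 6.1 adds a rule at patient level: "each patient must provide both a pre- and post-surgery sample (optional blood will be allowed) in order to be used in the signature analyses". A patient whose post-surgery collection is missing or unsatisfactory is replaced, and enrolment runs until 90 patients have both. What makes a collection unsatisfactory is not stated.

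The footnotes in 4.3 give a minimum only for saliva (2 ml) and urine (25 ml). For EBC there is an expected yield, "Approximately 1-1.5 mL of EBC will be generated in 10 min of breathing"; for EBV a collected volume (500 ml on each of four tubes); for blood a range (5-10 ml per tube).

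**The concern.** The protocol itself expects acceptance to differ by type, since it makes blood optional, yet the planned primary estimates merge all types. If any one specimen makes a provider, the count says little about the breath devices. If all are needed, the worst collection drives it. Two analysts following 5.1.1.1 and 6.2 could report very different feasibility from the same patients. The denominator of 5.1.1.1.4 and the point at which enrolment ends depend on the same undefined term.

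The rule in 6.1 raises a second problem. If it requires every specimen except blood, a failed breath collection takes the patient's valid saliva and urine pairs out of the signature analyses. The assays give no reason for that. The research data part of 4.2 runs breath on one platform, saliva, serum, urine and tissue metabolomics on others, and the microbiome work on blood, saliva and tumour; 6.3 tests markers one at a time.

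**Working it through.** **The plan's own figures.** Clopper-Pearson limits for the scenarios in 6.1:

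- 90/120: 0.663 to 0.825 (plan: 0.66, 0.82)
- 90/150: 0.517 to 0.679 (plan: 0.52, 0.68)
- 90/180: 0.425 to 0.575 (plan: 0.42, 0.58)

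Paired t-test power with 90 pairs, 0.30 SD and two-sided alpha 0.05 is 0.804 (plan: 80%). All reproduce, so the defect is one of definition and not of arithmetic.

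**Any versus all at one visit.** Inputs: four non-optional types (EBV, EBC, saliva, urine; 4.3, with blood optional in 4.2.2) and a success rate p per type. The documents give no p, so 80% and 90% are assumptions, as are equality and independence. Any = 1 - (1 - p)^4; all = p^4.

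- p = 0.90: any = 1 - 0.1^4 = 99.99%; all = 0.9^4 = 65.6%
- p = 0.80: any = 1 - 0.2^4 = 99.8%; all = 0.8^4 = 41.0%

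These apply to patients who attend the visit. The post-surgery count also contains missed visits. If 75% attended (an assumption that borrows the completion rate in 6.4) and p = 0.90, any = 0.75 x 0.9999 = 75.0% and all = 0.75 x 0.656 = 49.2%. The gap narrows but remains.

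**What a composite reveals without independence.** A count of 90/120 = 75% is compatible with any single collection succeeding in 75% to 100% of patients if all are required, or in 0% to 75% if any one suffices. Feasibility by type cannot be recovered from it.

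**Enrolment if all four are required at both visits.** Complete = p^8; patients needed = 90/p^8, rounded up, under the same assumptions.

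| p per type per visit | complete | patients for 90 |
|---|---|---|
| 0.99 | 92% | 98 |
| 0.95 | 66% | 136 |
| 0.90 | 43% | 210 |
| 0.85 | 27% | 331 |

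At p = 0.90 the 210 patients exceed the largest scenario in 6.1 (180). At 2 per week they take 210/2 = 105 weeks, against a longest anticipated 90 weeks in 6.4.

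**Pairs set aside on the all-required reading.** If breath fails in a fraction f of otherwise complete patients, reaching 90 takes 90/(1 - f) of them, rounded up, and the excess over 90 have valid saliva and urine pairs that are not used. For f = 5%, 10%, 20% and 25% (assumed) the totals are 95, 100, 113 and 120, so 5, 10, 23 and 30 pairs are set aside.

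**After the change.** With 120 patients, exact intervals by type would be 0.894 to 0.981 for 114/120, 0.832 to 0.947 for 108/120 and 0.717 to 0.867 for 96/120. Each is narrower than the plan's 90/120 row. If 100 to 120 pairs of a type were available, power at 0.30 SD would be 0.84 to 0.90, against 0.80 with 90.

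**The case against.** The best reply is that feasibility is framed as adding a package of collections to two visits, and that a funnel ending in 90 completers answers that. The documents do frame it so. A reader might infer that choosing which collections to keep is the pilot's stated purpose, but no section says this; 6.1 speaks of how many patients are needed and of ranking markers for future studies. Reporting by type is therefore a needed clarification of the primary outcome, not the recovery of a purpose the protocol states.

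A reader might also infer that valid pairs will be discarded. That is not established. Section 6.1 speaks of a sample in the singular, 6.3 examines each marker measured at both visits, and 4.2.2 banks all samples. Exempting only blood, together with replacement for an unsatisfactory collection, makes the all-required reading more likely but does not settle it. On the any-sample reading the loss of pairs falls away, and the primary count becomes uninformative about breath. That the rule selects a distorted signature set is also not shown: the documents give neither a direction nor a size.

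It would go too far to say the trial could never report by type. Section 7.0 lists a Specimen Collection Form that might allow it afterwards. Its fields are not given and no planned analysis uses it.

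Finally, the success rates are assumed, and independence is doubtful because attendance is common to all specimens at a visit. If failures cluster in the same patients, any and all move closer together. The rates illustrate the ambiguity and do not estimate it.

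**Conclusion.** The point holds for what is planned. Sections 5.1.1.1.3-4, 6.1 and 6.2 give one undifferentiated count per visit for five collections, do not define a provider, and so cannot show which collections are feasible. That conclusion needs no assumed rate. The size of the ambiguity does: 99.99% against 65.6% at 90% success per type, and 99.8% against 41.0% at 80%, for one visit's attenders with independent failures. The loss of valid saliva and urine pairs depends on the more likely reading of 6.1; on that reading it is about 5 to 30 pairs if breath fails in 5% to 25% of otherwise complete patients. The primary outcome should be defined before data are summarised; the plan's interval and power figures stand.

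**What to change.** - **5.1.1.1.3-4 and 6.2:** define what makes a patient a provider. Report the proportion and exact Clopper-Pearson interval for EBV, EBC, saliva, urine and blood separately, at each visit and as a pre/post pair. Keep all non-optional types together as the summary.
- **Adequacy:** use the minimums already in 4.3 for saliva (2 ml) and urine (25 ml). The sponsor should state criteria for EBV, EBC and blood, for which 4.3 gives no minimum, and refer to the same criteria where 6.1 speaks of unsatisfactory collections.
- **6.1:** analyse each specimen type in all patients with a valid pre/post pair of that type, whether or not another type failed, so that 6.1 and 6.3 agree.
- **7.0:** confirm that the Specimen Collection Form records each type at each visit.

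The cost is wording and some table rows, with no change in sample size. The small downside is that pair counts will differ across types and must be shown with each result. If the form does not record each type, it needs added fields.
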